11.0 STATISTICAL AND QUANTITATIVE ANALYSES

11.1. Determination of Sample Size

The Pilot portion of this study will determine if 1000 mg PLX3397 is an appropriate dose for the Phase II portion of the study. Traditional 3+3 design will be utilized to determine RP2D.

Eligible patients will enter the study in sets of three. Dose-limiting toxicity (DLT) is defined in Section 7.4. If 0 or 1 of 3 patients at the 1000 mg dose level cohort experience DLT, 3 additional patients will be enrolled for a total of 6 patients. If ≥ 2 of 6 patients experience DLT at the 1000 mg dose, the dose will be de-escalated to 800 mg per day. If 0 or 1 of 3 patients at the 800 mg dose level cohort experiences DLT, 3 additional patients will be enrolled for a total of 6 patients. If ≥ 2 of 6 patients experience DLT at the 800 mg dose, the study will be terminated due to intolerability. Each cohort of patients will be observed for toxicity for 28 days in order to allow time to identify all acute effects of PLX3397. Between 6 and 12 patients will be accrued for the Pilot portion of this study.

The primary objective of the Phase II portion of this study is to evaluate the objective response rate (ORR) at the RP2D. The RP2D will be either the MTD or the alternate dose level below the MTD determined by sponsor and investigator. A true response rate of 40% or more will be considered promising while 15% or lower will not be considered as evidence of activity.

A Simon two-stage design with 90% targeted power and one-sided type I error of 5% will be employed for this study. With the assumption of 10% drop-out, the total sample size will be 32 patients to achieve 29 evaluable patients. During stage one, 13 evaluable patients will be enrolled. If there are 3 or more responses (CR+PR) observed, then the study will continue to the second stage of accrual, and 16 evaluable patients will be enrolled in the second stage. If there are 8 or more responses observed among 29 evaluable patients, the treatment will be considered promising.

With this design, the probability of terminating the study after 13 patients is 69% if the true response rate is 15%. The probability that the treatment will be considered promising is 5%, if the true response rate is 15%, and 90.7% if the true response rate is 40%. Allowing for a 10% unevaluability rate, the overall accrual goal will be 32 patients for the Phase II portion of this study.

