11.3. Populations for Analysis

The primary population for safety will consist of patients who signed the informed consent and have any follow-up data after receiving at least one dose of study drug. The primary population for efficacy will consist of the modified ITT population, i.e., patients who a) fulfill inclusion/exclusion criteria, b) have a baseline CT scan at screening, and c) have at least one on-study CT scan to assess tumor response to study drug, or early progression of disease or death prior to first tumor assessment during treatment period.

The main study will be closed at the cut-off date and the data will be followed in ongoing subjects in the extension part. Data collected in the extension part will be reported separately from the clinical study report.

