11.7. Efficacy Analysis

The Phase II portion of the study will follow a Simon two-stage design to compare a null ORR of 15% with an alternative ORR of 40% with 90% power and a one-sided type I error of 5%. The total sample size will be 29 evaluable patients. Thirteen patients will be enrolled in the first stage, with at least three responses required to proceed to the second stage. Eight responses among 29 patients are required for PLX3397 to be considered promising. See Section 11.10 for discussion of interim analysis.

Object tumor response to treatment will be evaluated using investigator-determined RECIST v1.1 ([ATTACHMENT 3](#)). PFS, OS and duration of response will be evaluated as secondary efficacy endpoints. PFS will be calculated for each patient as the number of days from study

enrollment to the date of the first documented disease progression or date of death from any cause, whichever occurs first. Overall survival is defined as the time from study enrollment to death from any cause, censoring at the date of last contact or the end of the study. Duration of response (DoR) is defined as the time from the first documentation of objective tumor response (CR or PR) that is subsequently confirmed to the first documentation of disease progression or to death due to any cause, whichever occurs first. DoR will only be calculated for the subgroup of patients with a confirmed objective tumor response. Sponsor may request imaging data for the confirmation of the tumor response.

The Kaplan-Meier method will be used to estimate the median PFS, OS and DoR.

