11.10. Interim Analysis

The Phase II portion of the study will follow a Simon two-stage design to compare a null ORR of 15% with an alternative ORR of 40% with 90% power and a one-sided type I error of 5%. The total sample size will be 29 evaluable patients. Thirteen patients will be enrolled in the first stage before triggering an interim analysis. At least three responses are required to proceed to the second stage. Eight responses among 29 patients are required for PLX3397 to be considered promising.

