If a new lesion is equivocal, for example because of its small size, continued therapy and follow-up evaluation will clarify if it represents truly new disease. If repeat scans confirm there is definitely a new lesion, then progression should be declared using the date of the initial scan.

(18) F-Fluorodeoxyglucose Positron Emission Tomography (FDG-PET)

While FDG-PET response assessments need additional study, it is sometimes reasonable to incorporate the use of FDG-PET scanning to complement CT scanning in assessment of progression (particularly possible ‘new’ disease). New lesions on the basis of FDG-PET imaging can be identified according to the following algorithm:

- Negative FDG-PET at baseline, with a positive FDG-PET at follow-up is a sign of PD based on a new lesion.
- No FDG-PET at baseline and a positive FDG-PET at follow-up:
 - If the positive FDG-PET at follow-up corresponds to a new site of disease confirmed by CT, this is PD.
 - If the positive FDG-PET at follow-up is not confirmed as a new site of disease on CT, additional follow-up CT scans are needed to determine if there is truly progression occurring at that site (if so, the date of PD will be the date of the initial abnormal FDG-PET scan).
 - If the positive FDG-PET at follow-up corresponds to a pre-existing site of disease on CT that is not progressing on the basis of the anatomic images, this is not PD.

Evaluation of best overall response

The best overall response is the best response recorded from the start of the study treatment until the end of treatment taking into account any requirement for confirmation. On occasion a response may not be documented until after the end of therapy so protocols should be clear if post-treatment assessments are to be considered in determination of best overall response. Protocols must specify how any new therapy introduced before progression will affect best response designation. The patient's best overall response assignment will depend on the findings of both target and non-target disease and will also take into consideration the appearance of new lesions. Furthermore, depending on the nature of the study and the protocol requirements, it may also require confirmatory measurement. Specifically, in non-randomised trials where response is the primary endpoint, confirmation of PR or CR is needed to deem either one the 'best overall response'. This is described further below.

Time point response

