It is assumed that at each protocol specified time point, a response assessment occurs. [Table 19-1](#) provides a summary of the overall response status calculation at each time point for patients who have measurable disease at baseline.

When patients have non-measurable (therefore non-target) disease only, [Table 19-2](#) is to be used.

Missing assessments and not-evaluable designation

When no imaging/measurement is done at all at a particular time point, the patient is not evaluable at that time point. If only a subset of lesion measurements are made at an assessment, usually the case is also considered not evaluable at that time point, unless a convincing argument can be made that the contribution of the individual missing lesion(s) would not change the assigned time point response. This would be most likely to happen in the case of PD.

For example, if a patient had a baseline sum of 50 mm with three measured lesions and at follow-up only two lesions were assessed, but those gave a sum of 80 mm, the patient will have achieved PD status, regardless of the contribution of the missing lesion.

If one or more target lesions were not assessed either because the scan was not done, or could not be assessed because of poor image quality or obstructed view, the Response for Target Lesions should be “Unable to Assess” since the patient is not evaluable. Similarly, if one or more non-target lesions are indicated as ‘not assessed’, the response for non-target lesions should be “Unable to Assess” (except where there is clear progression). Overall response would be “Unable to Assess” if either the target response or the non-target response is “Unable to Assess” (except where this is clear evidence of progression) as this equates with the case being not evaluable at that time point.

Best overall response: all time points

The *best overall response* will be determined by statistical programming once all the data for the patient is known.

Table 19-1: Time Point Response: Patients with Targets (+/- Non-Target) Disease

Target Lesions	Non-Target Lesions	New Lesions	Overall Response
CR	CR	No	CR
CR	Non-CR/non-PD	No	PR
CR	Not evaluated	No	PR
PR	Non-PD or not all evaluated	No	PR
SD	Non-PD or not all evaluated	No	SD
Not all evaluated	Non-PD	No	NE
PD	Any	Yes or No	PD
Any	PD	Yes or No	PD
Any	Any	Yes	PD

CR = complete response; PR = partial response; SD = stable disease; PD = progressive disease;
 NE = inevaluable

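### The stage-1 look has no stated confirmation rule and no minimum follow-up, so the plan's 5% error and 90.7% power are correct but not assured

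*Combined protocol and SAP*

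**What the plan says.** **Decision rules.** Section 11.1 sets the design: "A Simon two-stage design with 90% targeted power and one-sided type I error of 5% will be employed for this study". The two reference rates are given as "A true response rate of 40% or more will be considered promising while 15% or lower will not be considered as evidence of activity". The go rule reads "If there are 3 or more responses (CR+PR) observed, then the study will continue to the second stage of accrual", and eight or more responses among 29 evaluable patients count as promising. Section 10.2 defines ORR as CR plus PR by RECIST v1.1. Neither section mentions confirmation.

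**Confirmation.** Section 11.7 evaluates response by investigator RECIST v1.1 and points to Attachment 3. That attachment says that "in non-randomised trials where response is the primary endpoint, confirmation of PR or CR is needed to deem either one the" best overall response. It supplies Table 19-3 for the purpose and adds that best overall response "will be determined by statistical programming once all the data for the patient is known". Section 11.7 itself mentions confirmation only in connection with duration of response: "DoR will only be calculated for the subgroup of patients with a confirmed objective tumor response".

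**Timing of the look.** The synopsis (Section 2.0) and Section 5.1 place it after about 13 patients have been treated. Section 11.10 says "Thirteen patients will be enrolled in the first stage before triggering an interim analysis". Section 11.1 speaks of 13 evaluable patients. The nearest definition of evaluable is the efficacy population in Section 11.3: patients must "have at least one on-study CT scan to assess tumor response to study drug", or have early progression or death.

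**Scans.** Table 2-2, footnote 12, schedules CT every 8 weeks for the first 24 weeks, then every 12. PET is done at Cycle 2 Day 1 in the first 13 Phase II patients (footnote 15). The synopsis and Section 5.1 let a stage-1 response be based on RECIST or on PET.

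**The concern.** The error rates of a two-stage design rest on one definition of response, applied to the null rate, the alternative rate and both counts, with outcomes complete at each look. Here the definition has to be inferred, and the two places that mention confirmation pull apart. Attachment 3 implies that ORR is confirmed. Section 11.7, by naming confirmation only for duration of response, invites the opposite reading.

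The triggers do not allow for confirmation either. None of the three guarantees a second CT, and no text holds stage-2 accrual while scans are outstanding. A team that counts confirmed responses on the stated trigger can score recently entered patients as non-responders only because their second CT is not due, and so stop an active drug. The PET wording adds a second inconsistency: a PET finding at about week 4 precedes the first scheduled CT at about week 8 and is not the endpoint in Section 10.2.

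**Working it through.** **Inputs from Section 11.1.** n1 = 13, continue if X1 ≥ 3; n2 = 16, promising if X1 + X2 ≥ 8; p0 = 0.15, p1 = 0.40.

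**1. The plan's own figures.** With X1 ~ Bin(13, p) and X2 ~ Bin(16, p):

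- P(stop at stage 1) = P(X1 ≤ 2). At p = 0.15 this is 0.1209 + 0.2774 + 0.2937 = 0.692, against 69% stated.
- P(promising) = Σ over x = 3 to 13 of P(X1 = x) · P(X2 ≥ 8 − x). At p = 0.15 it is 0.04999, against 5% stated. At p = 0.40 it is 0.9069, against 90.7% stated.

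All three reproduce. P(go) at 40% is 0.942.

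**2. Earliest confirmation.** Scheduled CTs fall at weeks 8, 16 and 24, then every 12 weeks. A response first seen at week 8 is confirmed at week 16. One first seen at week 16 is confirmed at week 24. Attachment 3 sets no confirmation interval, so this spacing comes from the routine schedule only; unscheduled scans are not excluded.

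**3. A confirmed-only look with k patients not yet scoreable.** Suppose k of the 13 cannot yet have a confirmed response, the count is taken anyway, and fewer than 3 means a final stop. The values of k are assumptions.

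- P(go) = P(Y ≥ 3), with Y ~ Bin(13 − k, p).
- P(promising) = Σ over y ≥ 3 of P(Y = y) · P(Z ≥ 8 − y), with Z ~ Bin(16 + k, p). The k pending patients are scored by the final count.

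| k | P(go) at 40% | Power at 40% | Type I error at 15% |
|---|---|---|---|
| 0 | 94.2% | 90.7% | 5.0% |
| 2 | 88.1% | 85.5% | 4.2% |
| 3 | 83.3% | 81.1% | 3.7% |
| 4 | 76.8% | 75.1% | 3.2% |

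For k = 3, the stop probability at 40% is 0.0060 + 0.0403 + 0.1209 = 0.167, against 0.058 in the plan. The damage is lost power; the type I error falls.

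**4. Other readings, with the same exact sums.** Let c be the share of responses that are later confirmed, again an assumption.

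- Unconfirmed responses counted at stage 1 and confirmed ones at the end, with 15% and 40% as confirmed rates and c from 0.9 down to 0.6: type I error 5.1% to 5.6%, power 92.5% to 94.3%. With no stage-1 stop at all, the limits are 5.86% and 94.3%.
- Unconfirmed responses counted at both looks, with 15% as a confirmed rate: the null rate on the counted scale is 0.15/0.9 = 0.167 or 0.15/0.8 = 0.1875, and the type I error is 8.3% or 14.0%.

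**The case against.** The best defence is that confirmation is already built in by reference. Section 11.7 sends response to Attachment 3, which requires confirmation for this type of trial and supplies Table 19-3. On that reading the 8-of-29 count is consistent. The go rule is a count without a deadline, enrolment of 13 can be read as a precondition and not a data cut-off, and best response is settled when a patient's data are complete. No passage orders a decision while scans are outstanding. This stands to the extent that the stated error rates cannot be called wrong: a careful team could run the trial as written and obtain them. It does not remove the gap, because the plan nowhere tells the team to wait.

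Three stronger inferences are tempting and are not supported:

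- *The 5% and 90.7% do not hold.* They are exact, and they hold under one definition with complete stage-1 data.
- *The look can come before any CT.* The treated and enrolled wording would allow it, but Section 11.1 says 13 evaluable patients. Read with Section 11.3, that means at least one on-study CT, or early progression or death.
- *The type I error is inflated to 8.3% or 14.0%.* This needs unconfirmed counting at both looks, despite Attachment 3, and a 15% null that is a confirmed rate. No passage says on which scale the 15% was set. The mixed reading in step 4 moves the error very little.

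**Conclusion.** The point holds as a gap in the stopping rule, not as an error in the sample-size calculation. The definition of response for the two counts is left to inference, and none of the stated triggers ensures that all 13 patients could have been confirmed. If confirmed responses are counted on such a trigger, power at 40% is 85.5%, 81.1% or 75.1% with 2, 3 or 4 patients unscored, instead of 90.7%. This assumes that the stop is final and that the unscored patients count as non-responders at the look; how many would be unscored depends on accrual, which the documents do not give. The PET wording in the synopsis and Section 5.1 is a plain mismatch with Section 10.2.

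A reader might take this as a change that must be made before the trial proceeds. The documents do not support that. Section 5.1 reports that the sponsor discontinued the study after six Pilot patients, so no 3-of-13 or 8-of-29 decision is pending, although Version 9.0 keeps the Phase II design in its text.

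**What to change.** **Definition.** In the synopsis and Sections 5.1, 10.2, 11.1, 11.7 and 11.10, define a response for both counts as a confirmed CR or PR by RECIST v1.1 under Table 19-3. Delete the PET alternative from the stage-1 rule. State that 15% and 40% are rates on that definition. Report unconfirmed ORR as supportive.

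**Timing.** Replace the enrolled and treated triggers:

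- Decide *go* at the third confirmed response.
- Decide *stop* only when all 13 evaluable patients have had two post-baseline CTs or have progressed, died or stopped, and any response still unconfirmed at that point has had its next scheduled CT. Two CTs alone are not enough, because a first PR at week 16 cannot be confirmed on schedule until week 24.
- Hold stage-2 accrual until one of these is met, and apply the same minimum follow-up to the 8-of-29 count.

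A first response later than the second CT would still be missed at the look, so this bounds the under-count without removing every late responder.

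**Cost.** No extra patients or scheduled scans. When fewer than three responses are confirmed, the stage-1 decision comes about 16 − 8 = 8 weeks later than a look at the last patient's first CT, or about 16 weeks later than a look at enrolment. It takes longer if a first response at week 16 is pending. Stage-2 accrual waits in the meantime.

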11.2. Randomization and Stratification

No randomization or stratification of patients is planned for this study.

11.3. Populations for Analysis

The primary population for safety will consist of patients who signed the informed consent and have any follow-up data after receiving at least one dose of study drug. The primary population for efficacy will consist of the modified ITT population, i.e., patients who a) fulfill inclusion/exclusion criteria, b) have a baseline CT scan at screening, and c) have at least one on-study CT scan to assess tumor response to study drug, or early progression of disease or death prior to first tumor assessment during treatment period.

The main study will be closed at the cut-off date and the data will be followed in ongoing subjects in the extension part. Data collected in the extension part will be reported separately from the clinical study report.

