12. CT with and without contrast to assess tumor status will be performed every 8 weeks during the first 24 weeks of study treatment, then every 12 weeks thereafter (e.g., at the end of Cycles 2, 4, 6, then at the end of Cycles 9, 12, 15 and onward). PET/CT scan may be used as well.
13. Fresh tumor biopsy will be performed on Day 1 (-3d), Day 15 (-3d) (optional), and at the End-of-Study visit (optional) for first 13 patients enrolled in Phase II. Biopsies must be core needle or excisional (not fine needle), and sufficient for 20 unstained slides of 5 micron thickness. If a Screening tumor biopsy was obtained (Day -28 to Day -1), and there was sufficient tissue from that sample for laboratory testing, then tumor biopsy on Day 1 is not required. All PET scans should be performed prior to biopsy collection procedures to avoid false positive results.
14. Availability of archival tissue should be documented and at least 10 unstained slides of 5 micron thickness should be submitted to the central lab.
15. PET scan will be performed at Day 1 (-3d) of Cycle 1 or before fresh tumor biopsy in screening and Day 1 (± 3d) of Cycle 2 for the first 13 patients enrolled in the Phase II portion of the study. If a PET/CT scan is performed, then no additional PET scan is needed.
16. Assessments on these visits may be performed at a local hospital or testing facility for patient convenience. Results should be shared with the Principal Investigator within 48 hours.

17. ECOG Performance Status, symptom-directed physical examination, hematology, serum chemistry, and urinalysis do not need to be repeated if these assessments from Screening occurred within 3 days of C1D1 unless a change in status is suspected.
18. Drug Diary to be reviewed. Collection of completed drug diary and distribution of new diary to occur at beginning of each cycle.
19. Korea sites only. Whole blood for circulating tumor DNA assessment to be done pre-dose and the End of Study visit.
20. It could be more frequent if liver function test are elevated and reference the dose modification (Section 7.5).

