Based on the treatment emergent adverse event (TEAE) reports of increased INR observed in patients receiving concomitant warfarin, careful monitoring is required during treatment with pexidartinib. Warfarin doses should be adjusted if an increase in INR is noted.

Updated hepatic safety risk information as of December 2017; please consult the IB for more information: Hepatotoxicity is an important adverse drug reaction. Elevations of liver transaminases and bilirubin have been observed in studies with pexidartinib, together with cases of drug induced cholestasis. Cases of cholestasis have been observed in the first 8 weeks, have generally resolved with treatment discontinuation, but in some cases have been severe, with a protracted course requiring liver dialysis and, in 1 case, transplantation. Hepatotoxicity may be fatal. One fatal case with ongoing cholestatic liver injury at the time of death has been reported. Monitor patients closely as defined in the protocol. Protocol defined dose reductions and discontinuations of pexidartinib, increased frequency of laboratory monitoring, and reporting of findings should be followed (refer to Section 7.5). In addition, rechallenge with pexidartinib should not be attempted without prior discussion with the Sponsor's Medical Monitor.

Pexidartinib is a novel, orally active, small molecule inhibitor that targets CSF1R, Kit, and oncogenic Flt3, but remains highly selective versus other kinases. The potent inhibition of these 3 kinases can be exploited to attack tumors via multiple mechanisms. Pexidartinib has shown a potent inhibitor of the proliferation of these target dependent models.

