7.5. Dose-Modification Guidelines

Toxicities that occur outside the DLT window will be taken into consideration when determining the RP2D. Reduction/interruption of dosing for AEs may take place at any time. Below are guidelines for dosage modification for PLX3397–related toxicities as well as guidelines for their management. Dose reductions should occur in increments of 200 mg/day, depending on the toxicity grade, as noted in [Table 7-1](#) and [Table 7-2](#).

These parameters are only a guide and are not intended to supersede the clinical judgment of the treating physician. Medical Monitor should be notified of any dose adjustments. Dosing interruptions longer than 2 weeks for any reason should generally result in discontinuation from the study, unless the patient has demonstrated a clinical benefit from therapy and would like to continue dosing with study drug after discussion between the investigator and the Sponsor. Rechallenge with a reduced dose of pexidartinib may result in a recurrence of increased serum transaminases, bilirubin, or ALP. Monitor liver tests weekly for the first month after rechallenge.

Table 7-1: Dose Modification Guidelines for Treatment-emergent Toxicities

Adverse Reaction	Severity	Pexidartinib Dosage Modifications
Increased ALT and/or AST	Greater than 3 to 5 times ULN	
 • Withhold and monitor liver tests weekly. • If AST and ALT are less than or equal to 3 times ULN within 4 weeks, resume at reduced dose. • If AST or ALT is not less than or equal to 3 times ULN in 4 weeks, permanently discontinue pexidartinib.

	Greater than 5 to 10 times ULN	
 Withhold and monitor liver tests twice weekly. If AST and ALT are less than or equal to 3 times ULN within 4 weeks, resume at reduced dose. If AST or ALT is not less than or equal to 3 times ULN in 4 weeks, permanently discontinue pexidartinib.
	Greater than 10 times ULN	
 Permanently discontinue pexidartinib. Monitor liver tests twice weekly until AST or ALT is less than or equal to 5 times ULN, then weekly until less than or equal to 3 times ULN.
Increased ALP and Gamma-glutamyl transpeptidase (GGT)	ALP greater than 2 times ULN with GGT greater than 2 times ULN	
 Permanently discontinue pexidartinib. Monitor liver tests twice weekly until ALP is less than or equal to 5 times ULN, then weekly until less than or equal to 2 times ULN.

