9.2.12. End-of-Study visit

The End-of-Study visit is scheduled within the 28-day period after the last dose of study drug and before starting any new anti-neoplastic therapy.

Procedures to be performed:

- Fresh tumor biopsy (optional, first 13 patients enrolled in Phase II; –3-day window)
- Weight
- Physical examination (complete)
- 12-lead ECG
- Whole blood for ctDNA Korea sites only.
- Serum chemistry, including sodium, potassium, chloride, CO₂, calcium, phosphorus, glucose, BUN, creatinine, uric acid, total protein, albumin, total and direct bilirubin, AST, ALT, alkaline phosphatase, GGT, and LDH;
- Hematology: hemoglobin, hematocrit, white blood cell count with a differential, platelet count
- Vital signs, including blood pressure, respiratory rate, pulse rate, and body temperature;
- ECOG performance status assessment

- Adverse event assessment
- Concomitant medications

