11.4. Procedures for Handling Missing, Unused, and Spurious Data

All available efficacy and safety data will be included in the data listings and tabulations. No imputation of values for missing data will be performed.

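### Section 11.3 keeps early progressions and deaths in the ORR denominator but drops other treated patients with no on-study CT, which can raise ORR if those patients respond less often

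*Combined protocol and SAP*

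**What the plan says.** Section 11.3 sets three conditions for the primary efficacy (modified ITT) population: eligibility, a baseline CT, and a third condition that the patient "have at least one on-study CT scan to assess tumor response to study drug, or early progression of disease or death" before the first tumor assessment. Stopping for any other reason without a scan is not listed.

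- **Scan timing.** Table 2-2, footnote 12: "CT with and without contrast to assess tumor status will be performed every 8 weeks during the first 24 weeks of study treatment". The first scheduled on-study CT is thus at the end of Cycle 2.
- **After stopping.** Section 9.2.12: "The End-of-Study visit is scheduled within the 28-day period after the last dose of study drug". Its procedure list has no CT, and later follow-up is by remote contact only (the Post-Study Follow-up section).
- **Counting rule.** Section 11.1: "During stage one, 13 evaluable patients will be enrolled", followed by 16 more to reach 29, with at least 3 and then at least 8 responses required. Also in 11.1: "Allowing for a 10% unevaluability rate, the overall accrual goal will be 32 patients for the Phase II portion of this study". The section does not define evaluable.
- **Missing data.** Section 11.4: "No imputation of values for missing data will be performed".
- **Replacement.** Section 8.4 offers discretionary replacement for withdrawals other than for toxicity or clinically significant progression.
- **Liver toxicity.** Section 3.3: "Cases of cholestasis have been observed in the first 8 weeks, have generally resolved with treatment discontinuation". Table 7-1 in Section 7.5 orders immediate permanent discontinuation for ALT or AST above 10 times ULN, for ALP and GGT both above 2 times ULN, and for total bilirubin at or above 2 times ULN. For smaller transaminase rises it adds: "If AST or ALT is not less than or equal to 3 times ULN in 4 weeks, permanently discontinue pexidartinib".

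**The concern.** The rule keeps two kinds of early failure (progression and death) and leaves out a third: a treated patient who stops, alive and unprogressed, before any scan. Such stops are foreseeable, because known liver toxicity falls in the first 8 weeks and Table 7-1 makes some findings grounds for immediate discontinuation.

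ORR is the primary endpoint and decides both stages. Removing patients who respond less often than the rest raises the observed ORR, makes it easier to pass stage 1, and raises the chance of declaring an inactive drug promising. With no imputation and no all-treated ORR planned, nothing in the analysis would show the effect.

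**Working it through.** **Inputs from the plan (11.1).** Null ORR 15%, alternative 40%; continue with at least 3 responses in 13; promising with at least 8 in 29; 10% unevaluable, accrual goal 32.

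**Step 1: reproduce the design.** At response rate p:

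- stage 1 stop = P(Bin(13, p) ≤ 2)
- P(promising) = Σ over x = 3 to 13 of P(Bin(13, p) = x) × P(Bin(16, p) ≥ 8 − x)

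At p = 0.15 the stage 1 stop is 69.2% and P(promising) is 5.0%. At p = 0.40, P(promising) is 90.7%. All three match 11.1.

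**Step 2: ORR among those kept.** Let f be the share of treated patients removed and r their response rate. With 15% ORR in all treated patients, ORR among those kept is q = (0.15 − f·r)/(1 − f).

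The documents give no rate of stops before the first scan, so f is an assumption: 5% to 10%, that is, half to all of the plan's allowance for every cause (3/32 = 9.4%).

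With evaluable read as meeting 11.3, and accrual continuing until 29 such patients are reached:

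| f | r | q | P(promising) | Stage 1 stop |
|---|---|---|---|---|
| any | 15% | 0.1500 | 5.0% | 69.2% |
| 5% | 10% | 0.145/0.95 = 0.1526 | 5.5% | 68.2% |
| 10% | 10% | 0.140/0.90 = 0.1556 | 6.0% | 67.1% |
| 5% | 0 | 0.150/0.95 = 0.1579 | 6.4% | 66.2% |
| 10% | 0 | 0.150/0.90 = 0.1667 | 8.3% | 62.8% |

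The r = 0 rows have some basis in the plan. Attachment 3 takes best response only up to the end of treatment, so a patient never assessed has no recorded CR or PR.

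**Step 3: how accrual is read (r = 0).** Each treated patient is removed with probability f, responds with probability 0.15, or is a scanned non-responder with probability 0.85 − f. Following the count patient by patient gives:

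| Reading | f = 5% | f = 10% | Stage 1 stop |
|---|---|---|---|
| Accrue to 13, then 29 evaluable, no ceiling | 6.4% | 8.3% | 66.2% / 62.8% |
| Same, but total accrual held to 32 | 6.3% | 7.5% | 66.2% / 62.8% |
| Held to 32, and stage 1 counts 13 treated | 6.1% | 6.9% | 69.2% |

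The last row is a possible reading of the Synopsis and 5.1, which place the first analysis after about 13 patients have been treated.

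**Step 4: effect on the estimate.** Eight responses read as 8/29 = 27.6%. If the 3 planned unevaluable patients were all unscanned non-responders, the figure over all accrued would be 8/32 = 25.0%.

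**Step 5: with these patients counted.** The response rate in the 29 counted is then the all-treated rate. Type I error returns to 5.0% at 15%. If 40% is the ORR among scanned patients, the counted rate is 0.40 × 0.95 = 0.38 or 0.40 × 0.90 = 0.36, and power is 87.1% or 82.5%. If 40% applies to all treated patients, power stays at 90.7%.

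**The case against.** The strongest reply is that this is a choice of target, not a mistake. The plan openly sets its thresholds on evaluable patients, allows for 10% unevaluable, and already counts early progressions and deaths. For ORR among evaluable patients the design holds its 5.0%; inflation appears only when the 15% null is applied to all treated patients. That stands, and it limits the claim: the plan's operating characteristics are correct for the population it defines.

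A reader might infer that true type I error is 8.3%. The documents do not support that. The figure needs every unevaluable patient to be an unscanned non-responder, and it needs accrual past the stated goal of 32. A reader might also infer that toxicity stops are certain to be replaced. Section 8.4 frames replacement for other reasons; the place is refilled only if evaluable in 11.1 means meeting 11.3 and accrual continues to that count.

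The route out of the denominator is also narrower than the schedule suggests. Section 11.3 does not require the on-study CT to be a scheduled one, so an unscheduled CT would qualify. In the first 13 Phase II patients, a Cycle 2 Day 1 PET done as PET/CT might qualify too, shortening the gap to about 4 weeks; 11.3 does not say. The 4-week transaminase rule leads to discontinuation before week 8 only if the hold begins by about week 4. The immediate-discontinuation rows of Table 7-1 are the firmer evidence.

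Finally, Section 5.1 records that the sponsor discontinued the study after 6 Pilot patients. That does not alter the text of 11.3, but it removes most of the practical weight.

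**Conclusion.** The point holds in a limited form. As written, 11.3 can remove eligible treated patients who stop without progression before any on-study CT, and nothing else in the plan counts them as non-responders. Whether that biases ORR depends on whether they respond less often than the rest, which the documents do not show.

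On the all-treated target, with an assumed 5% to 10% removed, type I error moves from 5.0% to between 5.5% and 6.0% if the removed respond at 10%, and to between 6.1% and 8.3% if none respond, across the accrual readings above. If removal is unrelated to response, or the target is evaluable patients only, there is no inflation. The fall in the stage 1 stop from 69.2% to 66.2% or 62.8% applies only if none of the removed respond and stage 1 counts evaluable rather than treated patients.

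It would be too strong to say that the stated 5% is wrong or that a reported result is biased. This is an inexpensive improvement of low priority.

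**What to change.** - **11.3:** keep every treated, eligible patient with a baseline CT but no on-study CT in the ORR denominator as a non-responder, whatever the reason for stopping. Limiting this to toxicity stops would still drop unscanned patients who withdraw or are lost, and the return to 5.0% relies on counting them all.
- **11.1:** count these patients toward the 13 and the 29 without replacement, and say that evaluable has this meaning. Cross-refer from 8.4 so that discretionary replacement does not remove anyone from the count.
- **11.4:** name this as the exception to the no-imputation rule.
- **Sensitivity analysis:** report ORR in the current 11.3 population.

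The cost is wording, an ORR that may read slightly lower, and the possibility that a patient whose tumor was shrinking at an early stop counts as a non-responder. Power is 87.1% or 82.5% (5% or 10% share) if 40% is the ORR among scanned patients, and unchanged at 90.7% if 40% applies to all treated patients. If that loss matters, 34 counted patients with at least 9 responses and stage 1 unchanged give 4.8% type I error and 89.1% or 84.9% power, for 5 more counted patients than 29.
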